12.4.4 Criteria for Defining the Severity of an Adverse Event

AEs, including abnormal clinical laboratory values, will be graded using the NCI-CTCAE guidelines (version 5.0). The items that are not stipulated in the NCI-CTCAE guidelines (version 5.0) will be assessed according to the criteria below and entered into the eCRF:

Table 10 Grading Scale Defining the Severity of an Adverse Event

Grade	Assessment Standard
1 - Mild	Asymptomatic or mild symptoms, clinical or diagnostic observations only; intervention not indicated
2 - Moderate	Minimal local or noninvasive intervention indicated; limiting age-appropriate instrumental ADL†
3 - Severe	Medically significant but not immediately life threatening, hospitalization or prolonged hospitalization indicated; disabling; limiting self-care ADL‡
4 - Life-threatening	Life threatening consequences, urgent intervention indicated
5 - Death	Death related to AE

ADL: activities of daily living; AE: adverse event.

†Instrumental ADL refer to preparing meals, shopping for groceries or clothes, using the telephone, managing money, etc.

‡Self-care ADL refer to bathing, dressing and undressing, feeding self, using the toilet, taking medications and not bedridden.

12.4.5 Reporting Procedures for Serious Adverse Events or Defect of Investigational Product

The investigator must complete and submit an SAE worksheet containing all information that is required by local and/or regional regulations to the sponsor by fax or email immediately (within 24 hours of awareness).

The SAE worksheet must be signed by a medically qualified investigator (as identified on delegation of authority log). Signature confirms accuracy and completeness of the SAE data as well as the investigator causality assessment including the explanation for the causality assessment.

For contact details, see Contact Details of Sponsor's Key Personnel. Fax or email the SAE/special situations worksheet to:

Astellas Pharma Global Development Inc.
Pharmacovigilance
North America [contact]
North America alternate [contact]
Email: [contact]

Specific to Japan:

In the case of a SAE or defect, the investigator or subinvestigator must report to the head of the study site and must contact the sponsor by fax or email immediately (within 24 hours of awareness).

The investigator should complete and submit JUTOKUNA YUUGAIJISHOU OYOBIFUGUAI HOUKOKUSHO or JUTOKUNA YUUGAIJISHOU HOUKOKUSHO containing all information that is required by the appropriate regulatory authorities to the sponsor by fax or email immediately (within 24 hours of awareness) and to the head of the hospital.

Fax or email JUTOKUNA YUUGAIJISHOU OYOBIFUGUAI HOUKOKUSHO or JUTOKUNA YUUGAIJISHOU HOUKOKUSHO and special situations worksheet to:

Astellas Pharma Inc. – Japan
Pharmacovigilance
[contact]
Email: [contact]

If there are any questions, or if clarification is needed regarding the SAE, please contact the sponsor's medical monitor/study physician or their designee [see Contact Details of Sponsor's Key Personnel].

Follow-up information for the event should be sent promptly (as soon as available, but no longer than within 7 days of the initial notification or for Japan sites, within 2 days for the initial notification).

Full details of the SAE should be recorded on the medical records, SAE/special situation worksheet and on the eCRF.

The following minimum information is **required**:

- International study number/study number
- Subject number, sex and age
- Date of report
- Description of the SAE (event and seriousness criteria) and defect (if applicable)
- Causal relationship to the IP (including reason)
- Drug provided (if any)

The sponsor or sponsor's designee will medically evaluate the SAE and determine if the report meets the requirements for expedited reporting based on seriousness, causality, and expectedness of the events (e.g., suspected unexpected serious adverse reactions [SUSAR] reporting) according to current local/regional regulatory requirements. The sponsor or sponsor's designee will submit expedited safety reports to CAs and concerned ethics committee per current local regulations, and will inform the investigators of such regulatory reports as required. Investigators must submit safety reports as required by their IRB/IEC within timelines set by regional regulations (e.g., EMA, FDA) where required. Documentation of the submission to and receipt by the IRB/ IEC of expedited safety reports should be retained by the study site. In the US, FDA expedited IND reporting guidelines will be followed.

The sponsor will notify all investigators responsible for ongoing clinical studies with the test product of all SUSARs, which require submission per local requirements IRB/IEC/head of the study site.

The heads of the study sites/investigators should provide written documentation of IRB/IEC notification for each report to the sponsor.

The investigator may contact the sponsor's medical monitor/study physician for any other problem related to the rights, safety or well-being of the subject.

12.4.6 Reporting Procedures for Special Situations

12.4.6.1 Pregnancy

If a female subject becomes pregnant during the study dosing period or within 180 days from the discontinuation of dosing, the investigator is to report the information to the sponsor according to the timelines in [Appendix 12.4.5 Reporting Procedures for SAEs or Defect of Investigational Product] using the SAE worksheet as a special situation and in the eCRF.

The investigator will attempt to collect pregnancy information on any female partner of a male subject who becomes pregnant during the study dosing period or within 180 days from the discontinuation of dosing and report the information to sponsor according to the timelines in [Appendix 12.4.5 Reporting Procedures for SAEs or Defect of Investigational Product] using the SAE worksheet as a special situation.

The expected date of delivery or expected date of the end of the pregnancy, last menstruation, estimated conception date, pregnancy result and neonatal data, etc., should be included in this information.

While pregnancy itself is not considered to be an AE or SAE, any pregnancy complication or termination (including elective termination) of a pregnancy is to be reported for a female subject as an AE in the eCRF or SAE per [Appendix 12.4.5 Reporting Procedures for SAEs or Defect of Investigational Product]. For (S)AEs experienced by a female partner of a male subject, (S)AEs are to be reported via the SAE worksheet.

Additional information regarding the outcome of a pregnancy when also categorized as an SAE is mentioned below:

- “Spontaneous abortion” includes miscarriage, abortion and missed abortion.
- Death of a newborn or infant within 1 month after birth is to be reported as an SAE regardless of its relationship with the IP.
- If an infant dies more than 1 month after the birth, it is to be reported if a relationship between the death and intrauterine exposure to the IP is judged as “possible” by the investigator.
- Congenital anomaly (including anomaly in miscarried fetus)

Unless a congenital anomaly is identified prior to spontaneous abortion or miscarriage, the embryo or fetus should be assessed for congenital defects by visual examination or other means as appropriate. (S)AEs experienced by the newborn/infant should be reported via the pregnancy reporting form. Generally, follow up will be no longer than 6 to 8 weeks following the estimated delivery date.

12.4.6.2 Medication Error, Overdose and “Off-label Use”

If a medication error (defined as an unintended failure in the treatment process that leads to, or has the potential to lead to, harm to the subject), overdose or “off-label use” (i.e., use outside of what is stated in the protocol) is suspected, refer to [Section 10.3 Major Protocol Deviations]. Any associated (S)AEs are to be reported in the eCRF. If the AE meets the definition of an SAE, the SAE is also to be reported as described in [Appendix 12.4.5 Reporting Procedures for SAEs or Defect of Investigational Product] together with the details of the medication error, overdose and/or “off-label use.”

No information on overdose of ASP7517 is available. As ASP7517 is administered intravenously, the pharmacy manual will provide detailed instructions for preparation to ensure that the correct dose is dispensed. In the event of an overdose, subjects should be managed by symptomatic and supportive care and observed in a controlled medical setting. In the event of suspected ASP7517 medication error, the subject should receive supportive care and monitoring. The medical monitor/expert should be contacted as applicable.

12.4.6.3 Misuse/Abuse

Definition of misuse: Situations where the IP is/are intentionally and inappropriately used not in accordance with the intended use as defined in the protocol.

Definition of abuse: Persistent or sporadic, intentional excessive use of medicinal products which is accompanied by harmful physical or psychological effects.

If misuse or abuse of the IP is suspected, the investigator must forward the special situation worksheet to the sponsor by fax or email immediately (within 24 hours of awareness). Any associated (S)AEs are to be reported in the eCRF. If the AE meets the definition of an SAE, the SAE is also to be reported as described in [Appendix [12.4.5](#) Reporting Procedures for SAEs or Defect of Investigational Product] together with details of the misuse or abuse of the IP.

12.4.6.4 Occupational Exposure

If occupational exposure (e.g., inadvertent exposure to the IP of study site personnel while preparing it for administration to the subject) to the IP occurs, the investigator must forward the special situation worksheet to the sponsor by fax or email immediately (within 24 hours of awareness). Any associated (S)AEs occurring to the individual associated with or resulting from the special situation are to be reported on the special situations worksheet.

12.4.6.5 (Suspicion of)Transmission of Infectious Agent

If transmission of an infectious agent related to the microbiological contamination at the site is suspected, the investigator must forward the special situation worksheet to the sponsor by fax or email immediately (within 24 hours of awareness) and any associated (S)AEs are to be reported in the eCRF. If the AE meets the definition of an SAE, the SAE is also to be reported as described in [Section [12.4.5](#) Reporting Procedures for SAEs or Defect of Investigational Product] together with the details of the suspected transmission of infectious agent.

12.4.6.6 Suspected Drug-drug Interaction

If a drug-drug interaction associated with the IP is suspected, the investigator must forward the special situation worksheet to the sponsor by fax or email immediately (within 24 hours of awareness). Any associated (S)AEs are to be reported in the eCRF. If the AE meets the definition of an SAE, the SAE is also to be reported as described in [Appendix [12.4.5](#) Reporting Procedures for SAEs or Defect of Investigational Product] together with details of the suspected drug-drug interaction.

12.5 Liver Safety Monitoring and Assessment

The purpose of this appendix is to provide guidance for the monitoring of drug-induced liver injury during the course of the study. It should be noted that this section does not specify the End of Study analyses of liver enzymes. The end of study liver enzymes analyses will be described in the SAP. Any subject enrolled in a study with active drug therapy and reveals an increase of serum aminotransferases (AT) to $> 3 \times$ ULN or bilirubin $> 2 \times$ ULN should undergo detailed testing for liver enzymes (including at least ALP, ALT, AST and TBL). Testing should be repeated within 72 hours of notification of the test results. Subjects should be asked if they have any symptoms suggestive of hepatobiliary dysfunction.

Definition of Liver Abnormalities

Confirmed abnormalities will be characterized as moderate and severe where ULN is as shown below.

Table 11 Moderate and Severe Liver Abnormalities

	ALT or AST		TBL
Moderate	$> 3 \times$ ULN	or	$> 2 \times$ ULN
Severe	$> 3 \times$ ULN	and†	$> 2 \times$ ULN

ALT: alanine aminotransferase; AST: aspartate aminotransferase; TBL: total bilirubin; ULN: upper limit of normal

†Samples taken simultaneously or within maximum 24 hours.

In addition, the subject should be considered to have severe hepatic abnormalities for any of the following:

- ALT or AST $> 8 \times$ ULN
- ALT or AST $> 5 \times$ ULN for more than 2 weeks.
- ALT or AST $> 3 \times$ ULN and† TBL $> 2 \times$ ULN or international normalized ratio (INR) > 1.5 (if INR testing is applicable/evaluated)
- ALT or AST $> 3 \times$ ULN with the appearance of fatigue, nausea, vomiting, right upper quadrant pain or tenderness, fever, rash and/or eosinophilia ($> 5\%$)

† Samples taken simultaneously or within a maximum of 24 hours.

The investigator may determine that abnormal liver function results, other than as described above, may qualify as moderate or severe abnormalities and require additional monitoring and follow-up.

Follow-up Procedures

Confirmed moderate and severe abnormalities in hepatic functions should be thoroughly characterized by obtaining appropriate expert consultations, detailed pertinent history, physical examination and clinical laboratory tests. The study site personnel are to complete the liver abnormality case report form (LA-CRF). Subjects with confirmed abnormal LFTs should be followed as described below.

Confirmed moderately abnormal LFTs should be repeated 2 to 3 times weekly, and then weekly or less if abnormalities stabilize or the IP has been discontinued and the subject is asymptomatic.

Severe hepatic liver function abnormalities as defined above, in the absence of another etiology, may be considered an important medical event and may be reported as a SAE. The sponsor should be contacted and informed of all subjects for whom severe hepatic liver function abnormalities possibly attributable to IP are observed.

To further assess abnormal hepatic laboratory findings, the investigator is expected to:

- Obtain a more detailed history of symptoms and prior or concurrent diseases. Symptoms and new-onset diseases are to be recorded as “AEs” within the eCRF. Illnesses and conditions such as hypotensive events, and decompensated cardiac disease that may lead to secondary liver abnormalities should be noted. Nonalcoholic steatohepatitis is seen in obese hyperlipoproteinemic and/or diabetic subjects, and may be associated with fluctuating AT levels. The investigator should ensure that the medical history form captures any illness that predates study enrollment that may be relevant in assessing hepatic function.
- Obtain a history of concomitant drug use (including nonprescription medication, complementary and alternative medications), alcohol use, recreational drug use and special diets. Medications are to be entered in the eCRF. Information on alcohol, other substance use and diet should be entered on the LA-CRF or an appropriate document.
- Obtain a history of exposure to environmental chemical agents.
- Based on the subject’s history, other testing may be appropriate including:
 - Acute viral hepatitis (A, B, C, D, E or other infectious agents)
 - Ultrasound or other imaging to assess biliary tract disease
 - Other clinical laboratory tests, including INR and direct bilirubin
- Consider gastroenterology or hepatology consultations.
- Submit results for any additional testing and possible etiology on the LA-CRF or an appropriate document.

Study Treatment Discontinuation

In the absence of an explanation for increased LFTs, such as viral hepatitis, preexisting or acute liver disease, or exposure to other agents associated with liver injury, the subject may be discontinued from study treatment. The investigator may determine that it is not in the subject’s best interest to continue study treatment. Discontinuation of study treatment should be considered if:

- ALT or AST $> 8 \times$ ULN
- ALT or AST $> 5 \times$ ULN for more than 2 weeks
- ALT or AST $> 3 \times$ ULN and† TBL $> 2 \times$ ULN or INR > 1.5 (if INR testing is applicable/evaluated)
- ALT or AST $> 3 \times$ ULN with the appearance of fatigue, nausea, vomiting, right upper quadrant pain or tenderness, fever, rash and/or eosinophilia ($> 5\%$)

† Samples taken simultaneously or within a maximum of 24 hours.

In addition, if close monitoring for a subject with moderate or severe hepatic laboratory tests is not possible, study treatment should be discontinued.

Hy's Law definition: Drug-induced jaundice caused by hepatocellular injury, without a significant obstructive component, has a high rate of bad outcomes, from 10% to 50% mortality (or transplant).

The 2 "requirements" for Hy's Law are:

1. Evidence that a drug can cause hepatocellular-type injury, generally shown by an increase in AT elevations $> 3 \times \text{ULN}$ (" $2 \times \text{ULN}$ elevations are too common in treated and untreated subjects to be discriminating").
2. Cases of increased TBL (at least $2 \times \text{ULN}$) with concurrent AT elevations at least $3 \times \text{ULN}$ and no evidence of intra- or extra-hepatic bilirubin obstruction (elevated ALP) or Gilbert's syndrome [Temple, 2006].

FDA Guidance for Industry titled, "Drug-induced Liver Injury: Premarketing Clinical Evaluation" issued by the FDA on July 2009:

1. The drug causes hepatocellular injury, generally shown by a higher incidence of 3-fold or greater elevations above the ULN of ALT or AST than the (nonhepatotoxic) control drug or placebo.
2. Among subjects showing such AT elevations, often with ATs much greater than $3 \times \text{ULN}$, 1 or more also show elevation of serum TBL to $> 2 \times \text{ULN}$, without initial findings of cholestasis (elevated serum ALP).
3. No other reason can be found to explain the combination of increased AT and TBL, such as viral hepatitis A, B, or C; preexisting or acute liver disease; or another drug capable of causing the observed injury.

References

Temple R. Hy's Law: Predicting Serious Hepatotoxicity. *Pharmacoepidemiol Drug Saf.* 2006;15(4):241-3.

12.6 List of Excluded Concomitant Medications

12.6.1 Concomitant Medications

The following list describes concomitant medications that are prohibited. This list should not be considered all inclusive. If there are concerns or questions about concomitant use of any drugs listed below, discussion with the medical monitor is strongly encouraged.

Drug Type	Generic Drug Name
Corticosteroids*	Dexamethasone Prednisone (Deltasone, Orasone, Predone, RAYOS, Sterapred, etc.)
Interferon/polyethylene-interferon	
Immunosuppressive Agents	Abatacept (Orencia, etc.) Adalimumab (Humira, etc.) Anajunra (Kineret, etc.) Azathioprine (Azasan, Imuran, etc.) Budesonide (Entocort EC, etc.) Certolizumab (Cimzia, etc.) Cyclosporine (Neoral, Sandimmune, SangCya, etc.) Etanercept (Enbrel, etc) Everolimus (Afinitor, Zortress, etc.) Golimumab (Simponi, etc.) Infliximab (Remicade, etc.) Ixekizumab (Taltz, etc.) Leflunomide (Arava, etc.) Mycophenolate (CellCept, Myfortic, etc.) Natalizumab (Tysabri, etc.) Prednisolone (Millipred, etc.) Rituximab (Rituxan, etc.) Secukinumab (Cosentyx, etc.) Sirolimus (Rapamune, etc.) Tocilizumab (Actemra, etc.) Tofacitinib (Xeljanz, etc.) Ustekinumab (Stelara, etc.) Vedolizumab (Entyvio, etc.)

*The use of high dose system corticosteroids are prohibited, with the exception of immune-related AEs (steroids can be used if not intended for treatment of AML or MDS; steroids for AML/MDS related symptoms can be used at low doses [less than 10 mg/day dexamethasone]).

12.6.2 Other Investigational Agents

Treatment with investigational agents other than ASP7517 is prohibited. If there are concerns or questions about concomitant use of these drugs, discussion with the co-chairs and protocol officer is strongly encouraged.

12.6.3 Other Treatments for Acute Myeloid Leukemia and/or Myelodysplastic Syndrome

Any other treatments of AML or MDS (including, but not limited to, chemotherapy, radiotherapy, surgery, immunotherapy and cellular therapy) are prohibited, with the following exceptions:

- Hydroxyurea up to 5 g daily for up to 2 weeks to keep the absolute blast count < 20,000/ μ L.
- Subject undergoing HSCT will be discontinued from the study.
- Intrathecal chemotherapy used as prophylaxis.

If there are concerns or questions about concomitant use of these drugs, discussion with the medical monitor is strongly encouraged.

12.7 Laboratory Assessments

Laboratory tests will be performed and analyzed by the institution's local laboratory according to the Schedules of Assessments [[Table 1](#) and [Table 2](#)] and results submitted for centralized data entry.

Additional laboratory tests should be performed according to the institutional standard of care.

Clinical significance of out-of-range laboratory findings is to be determined and documented by the investigator/or delegated subinvestigator who is a qualified physician.

Table 12 Clinical Laboratory Tests

Panel/Assessments	Parameters to be Analyzed
Hematology	Blast count and cell count Hematocrit (Hct) Hemoglobin (Hgb) Mean corpuscular volume (MCV) Mean corpuscular hemoglobin (MCH) Mean corpuscular hemoglobin concentration (MCHC) Platelet count Red blood cell count (RBC) White blood cell count (WBC) White blood cell count differential
Chemistry	Sodium (Na) Potassium (K) Chloride (Cl) Bicarbonate (HCO3) Blood urea nitrogen (BUN) Creatinine (Cr) Glucose (Gl) Calcium (Ca) Phosphate (Pi) Magnesium (Mg) Albumin (Alb) Total protein (T Prot) Alkaline phosphatase (ALP) Lactate dehydrogenase (LDH) Creatine phosphokinase (CK) Liver function tests including: Bilirubin total (TBL) Alanine aminotransferase (ALT) Aspartate aminotransferase (AST)
Table continued on next page	

Panel/Assessments	Parameters to be Analyzed
Urinalysis	Color Appearance Specific gravity pH Bilirubin Blood Glucose Ketones Leukocyte esterase Nitrite Protein Urobilinogen
Urine/Serum Pregnancy Test **	hCG
Coagulation Profile (PT/INR, D-Dimer, Fibrinogen)	Activated partial thromboplastin time (aPTT) International normalized ratio (INR) Prothrombin time (sec) (PT) Fibrinogen D-Dimer
Bone Marrow***	Blast count and cell counts * Flow cytometry for blasts
Blood Sample for Disease Assessment***	Blast count and cell counts

eCRF: electronic case report form; hCG: human chorionic gonadotrophin.

* In addition to the central read of these values, local results will also be collected and entered into the eCRF.

** Local results will be collected and entered into the eCRF.

*** Samples must be submitted to a central laboratory for analysis. Refer to the laboratory manual for additional information.

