7 STUDY PROCEDURES AND ASSESSMENTS

7.1 Efficacy Assessments

7.1.1 Response Criteria Definitions

7.1.1.1 Acute Myeloid Leukemia Response Criteria

Response to treatment will be defined per modified criteria [Cheson et al, 2003] as outlined below.

- Complete Remission (CR)

For subjects to be classified as being in CR at a post-baseline visit, they must have bone marrow regenerating normal hematopoietic cells and achieve a morphologic leukemia-free state and must have an absolute neutrophil count (ANC) $\geq 1 \times 10^9/L$ and platelet count $\geq 100 \times 10^9/L$, and normal marrow differential with $< 5\%$ blasts, and they will be red blood cell (RBC) and platelet transfusion independent (defined as 1 week without RBC transfusion and 1 week without platelet transfusion). There must be no presence of Auer rods. There should be no evidence of extramedullary leukemia. The blast counts in peripheral blood must be $\leq 2\%$.

- Complete Remission with Incomplete Platelet Recovery (CRp)

For subjects to be classified as being in CRp at a post-baseline visit, they must achieve CR except for incomplete platelet recovery ($< 100 \times 10^9/L$).

- Complete Remission with Incomplete Hematological Recovery (CRI)

For subjects to be classified as being in CRI at a post-baseline visit, they must fulfill all the criteria for CR except for incomplete hematological recovery with residual neutropenia (ANC $< 1 \times 10^9/L$) with or without complete platelet recovery. RBC and platelet transfusion independence is not required.

- Composite Complete Remission (CRC)

For subjects to be classified as being in CRC at a post-baseline visit, they must either achieve CR, CRp or CRI at the visit.

- Complete Remission with Partial Hematologic Recovery (CRh)

For subjects to be classified as CRh at a post-baseline visit, if they have marrow blasts $< 5\%$, partial hematologic recovery ANC $\geq 0.5 \times 10^9/L$ and platelets $\geq 50 \times 10^9/L$, no evidence of extramedullary leukemia and cannot be classified as CR. The blast counts in peripheral blood must be $\leq 2\%$.

- Partial Remission (PR)

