7.1.1.2 Myelodysplastic Syndrome Response Criteria

Response to treatment will be defined according to the modified International Working Group response criteria [Cheson et al, 2006] as outlined below.

- Complete Remission (CR)

For subjects to be classified as being in CR at a post-baseline visit, they must have all of the following maintained for a minimum of 4 weeks:

- Bone marrow evaluation: $\leq 5\%$ myeloblasts with normal maturation of all cell lines
- Peripheral blood evaluation:
 - Hemoglobin ≥ 11 g/dL
 - Platelets $\geq 100 \times 10^9/L$
 - Neutrophils $\geq 1.0 \times 10^9/L$
 - 0% blasts in blood

- Partial Remission (PR)

For subjects to be classified as being in PR at a post-baseline visit, they must have all CR criteria if abnormal before treatment except the following for a minimum of 4 weeks:

- Bone marrow blasts decreased by $\geq 50\%$ over pretreatment but still $> 5\%$
- Cellularity and morphology not relevant

- Marrow CR

For subjects to be classified as being in marrow CR at a post-baseline visit, they must have all of the following for a minimum of 4 weeks:

- Bone marrow: $\leq 5\%$ myeloblasts and decrease by $\geq 50\%$ over pretreatment
 - Peripheral blood: if HI responses, they will be noted in addition to marrow CR

- Hematologic Improvement (HI)

Requires 1 measurement of the following maintained for at least 8 weeks without ongoing cytotoxic therapy:

- HI – erythroid:

- Hemoglobin increase of ≥ 1.5 g/dL
or
- For RBC transfusions performed for hemoglobin ≤ 9.0 g/dL: reduction in RBC units transfused in 8 weeks by ≥ 4 units compared to the number of units transfused in the 8 weeks prior to treatment
- HI – platelets:
 - For pre-treatment platelet count of $>20 \times 10^9/L$ platelet, absolute increase of $\geq 30 \times 10^9/L$
 - For pre-treatment platelet count of $< 20 \times 10^9/L$, platelet absolute increase of $> 20 \times 10^9/L$ and $\geq 100\%$ increase from pre-treatment level
- HI – neutrophils:
 - Neutrophil count increase of $\geq 100\%$ from pre-treatment level and an absolute increase of $> 0.5 \times 10^9/L$

- **Relapse after CR or PR**
Requires at least 1 of the following:
 - Return to pre-treatment bone marrow blast percentage
 - Decrement of $\geq 50\%$ from maximum response levels in granulocytes or platelets
 - Transfusion dependence or hemoglobin level ≥ 1.5 g/dL lower than prior to therapy

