- Partial Remission (PR): For subjects to be classified as being in PR at a post-baseline visit, they must have bone marrow regenerating normal hematopoietic cells with evidence of peripheral recovery with no (or only a few regenerating) circulating blasts and with a decrease of at least 50% in the percentage of blasts in the bone marrow aspirate with the total marrow blasts between 5% and 25%. A value of less than or equal to 5% blasts is also considered a PR if Auer rods are present. There should be no evidence of extramedullary leukemia.
- Not Evaluable (NE)/No Response (NR): In the situation where no bone marrow assessments are performed or myeloblast value is missing, blast value from peripheral blood is missing or  $\leq 2\%$ , and extramedullary leukemia is missing or not present, the response will be

classified as NE. In any case response cannot be categorized as CR, CRp, CRi, PR or NE, it will be categorized as NR.

A complete response classification schema is presented in [Table 1](#), below.

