## 6.4 Analysis of Efficacy

Efficacy analyses will be conducted on the FAS and RAS. The interpretation of results from statistical tests will be based on the FAS. The RAS will be used to assess the robustness of the results from the statistical tests based on the FAS. All randomized subjects will be analyzed according to the treatment to which they are randomized/assigned. Efficacy data from the China cohort will be analyzed separately.

Derived response based on central assessment supplemented by local assessment: response will be derived based on the definitions in Section 7.1.1 using centrally evaluated myeloblast counts from bone marrow aspirate or biopsy assessments whichever is present (if both are present, both must qualify for the criteria) and centrally evaluated hematology results including ANC, platelet count and blast count in peripheral blood. If neither central bone marrow aspirate nor biopsy is available at baseline assessment, then myeloblast counts from locally evaluated bone marrow aspirate/biopsy assessments (if both are present, both must qualify for the criteria) will be used for all timepoints of assessment. Missing hematology results will not be imputed.

Derived response will be considered as primary and investigator reported response will be considered as supportive.

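### SAP Table 1 and SAP 6.4 leave the marrow-regeneration condition out of AML remission, so a hypocellular marrow with under 5% blasts counts as CRi in the primary CRc rate

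*Protocol*

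**What the plan says.** **Definition.** Protocol 7.1.1.1, repeated in SAP 5.1.1, says that for AML CR "they must have bone marrow regenerating normal hematopoietic cells and achieve a morphologic leukemia-free state". It also asks for ANC and platelet recovery, "and normal marrow differential with" fewer than 5% blasts, transfusion independence, no Auer rods, no extramedullary leukemia and at most 2% blood blasts. CRp is CR apart from platelets. CRi is CR apart from residual neutropenia, with or without platelet recovery, and for CRi "RBC and platelet transfusion independence is not required". CRc is any of the three and is the AML primary endpoint.

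**Derivation.** SAP 5.1.1 introduces Table 1 with the words "A complete response classification schema is presented in". Its columns are marrow myeloblasts, blood blasts, extramedullary disease, Auer rods, the two transfusion types, ANC and platelets. SAP 6.4 derives response from the definitions in a Section 7.1.1, "using centrally evaluated myeloblast counts from bone marrow aspirate or biopsy assessments whichever is present", together with central hematology. The derived response is primary; the investigator's is supportive.

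**Data listed.** The marrow row of protocol Table 12, and of SAP Table 5, reads "Blast count and cell counts * Flow cytometry for blasts". A footnote adds: "Samples must be submitted to a central laboratory for analysis. Refer to the laboratory manual for additional information".

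**MDS.** Under protocol 7.1.1.2, CR needs at most 5% "myeloblasts with normal maturation of all cell lines", plus recovered blood counts. Marrow CR needs only a blast level and a fall of at least half, and PR sets cellularity and morphology aside. The SAP has no MDS classification table.

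**The concern.** In the text definition of CRi, blood counts may stay low and transfusions may continue. What then separates a remission from a marrow that is merely empty is its quality: regeneration and a normal differential. Those are the conditions missing from the table that a programmer would code. Leaving out required conditions can only add responders, and the additions fall in CRc, which is judged against an inefficacious rate of 15% and a success count of 12 of 52.

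**Working it through.** **Step 1: definition against table, for CRi**

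| Condition | Text definition | SAP Table 1, CRi row |
|---|---|---|
| Marrow blasts | <5% | <5% |
| Marrow regenerating | required | no column |
| Normal differential | required | no column |
| Auer rods | absent | absent or missing |
| Extramedullary disease | absent | absent or missing |
| Blood blasts | ≤2% | missing or ≤2% |
| Transfusions | not required to be absent | no condition |
| ANC | <1 × 10^9/L | no condition |
| Platelets | any | no condition |

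**Step 2: one visit through both.** Take a hypocellular, non-regenerating marrow with <5% blasts, blood blasts ≤2%, no extramedullary disease, Auer rods not reported, ANC below 0.5 × 10^9/L, platelets below 50 × 10^9/L, transfused.

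- Text: it fails regeneration, so it is not CR, CRp or CRi. CRh fails on counts and PR also needs regeneration. The myeloblast value is present, so it is not NE. Result: no response.
- Table 1: it fails the CR, CRp and CRh rows on counts and meets every filled cell of the CRi row. Result: CRi, hence CRc.

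The CR and CRp rows still need ANC ≥1 × 10^9/L and no transfusions, so the route for an empty marrow is CRi.

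**Step 3: reproduce the plan's operating characteristics.** Inputs from protocol 9.1 and 9.4.1.3: stages of 12, 20 and 20; AML stops at ≤1 of 12 and ≤5 of 32; success at ≥12 of 52; rates 15% and 30%. With b(·) the binomial probability,

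P(success | p) = Σ over x ≥ 2 and x + y ≥ 6 of b(x; 12, p) · b(y; 20, p) · P[Bin(20, p) ≥ 12 − x − y].

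- p = 0.30: power 0.829 (stated: about 0.83).
- p = 0.15: type I error 0.067 (stated limit: 0.10).

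SAP 6.7 prints ≤6 of 32 for AML instead of ≤5. That gives power 0.801 and type I error 0.059 and does not reproduce 0.83, so the protocol boundaries are used here. The discrepancy is a separate matter to reconcile.

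**Step 4: illustration.** Assume a true CRc rate of 15% and d percentage points of non-responders classed as CRi. In 52 subjects each point is 0.52 of a subject, or 1/85 = 1.2% of true non-responders.

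| Assumed d | Observed CRc rate | Type I error, protocol boundaries | With SAP ≤6 of 32 |
|---|---|---|---|
| 0 | 15% | 0.067 | 0.059 |
| 1 | 16% | 0.097 | 0.087 |
| 2 | 17% | 0.136 | 0.122 |
| 3 | 18% | 0.181 | 0.163 |

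The 0.10 limit is passed between 1 and 2 points under either boundary.

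**Step 5: MDS.** A marrow at ≤5% blasts after a fall of at least half is marrow CR whatever its morphology. Maturation matters only when blasts are ≤5%, the fall is under half (for example 8% to 5%, a fall of 3/8 = 37.5%), and hemoglobin ≥11 g/dL, platelets ≥100 × 10^9/L, neutrophils ≥1.0 × 10^9/L and 0% blood blasts all hold for 4 weeks.

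**The case against.** The best defence is that SAP 6.4 invokes the full definitions. The SAP has no Section 7.1.1, but the protocol does, and it contains the regeneration requirement; SAP 5.1.1 repeats it. On that reading the text governs and Table 1 is shorthand. This does not settle the matter: Table 1 is presented as complete, and 6.4 names no marrow input other than myeloblast counts. At the least, text and algorithm disagree within the primary endpoint.

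A reader might go further and infer from Table 12 that morphology is never read. The documents do not support that. Table 12 is a list of laboratory parameters that refers onward to a laboratory manual we do not have. Protocol 7.2.2 sends local aspirate and biopsy results to the eCRF, and extramedullary disease and transfusions are recorded there although neither is in Table 12. The Auer-rod column of SAP Table 1 suggests that item is collected. What stands is that regeneration, if read, is not used.

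The frequency objection also stands. Protocol 5.2 excludes cytotoxic agents other than hydroxyurea within 28 days before the first dose, and protocol 6.5 restricts other AML therapy on study, though limited hydroxyurea is allowed. No figure is given for how often a hypocellular marrow with few blasts would occur. The investigator-reported response, kept as supportive, offers a partial cross-check.

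**Conclusion.** The point holds for AML. As written, the primary derivation does not apply the regeneration condition of its own definition, reads missing Auer rods as absent, and classes a non-regenerating marrow with <5% blasts and low counts as CRi. The direction is towards more responders; the size is unknown.

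Three stronger readings should not be drawn.

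- *That type I error is inflated to a known level.* The values in step 4 rest on assumed false-response rates. Protocol 9.1 does not say how the 15% was obtained; if it reflects comparable count-based response, no inflation follows.
- *That stage decisions are affected.* The documents do not say whether futility counts use the derived or the investigator's response.
- *That a dysplastic MDS marrow counts because morphology is skipped.* Marrow CR and PR admit it by definition, and no table overrides the text for MDS CR. Adding whole points to the 12% MDS rate has no basis; only the small group in step 5 could be affected.

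**What to change.** 1. In SAP Table 1, add a marrow-regeneration condition (yes/no, from the slide or biopsy already read) to the CR, CRp and CRi rows.
2. In SAP 6.4, name regeneration as an input and correct the section reference. Keep the existing source rule: central read, with local reads used throughout only when no central baseline marrow exists.
3. List regeneration and Auer rods as items of the marrow read in protocol Table 12 and SAP Table 5.
4. Report a sensitivity analysis of CRc in which visits with a missing regeneration or Auer-rod result do not qualify as remission. This is safer than deleting the missing category from the primary rows, which could discard true remissions.
5. For MDS, add one sentence to SAP 6.4 stating that CR applies the maturation condition.

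Sample size and boundaries do not change. The cost is one or two fields per marrow read and possibly a slightly lower CRc rate. Enrollment was planned from 3Q2019 and SAP version 3.0 is dated June 2023, so if the items were not captured, some would have to be recovered from existing reports or slides.
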